4. STUDY DESIGN

4.1. Overall Design

This is an open-label, single-dose study to assess the safety, tolerability, and PK of GSK3810109 administered SC with rHuPH20 or IV in healthy adult participants.

This study will comprise 3 parts:

In Part 1, approximately 8 participants will receive a single 20 mg/kg SC dose of GSK3810109 co-administered with rHuPH20 at dose of 2000 U/mL or ~28,000 U for a 70 kg participant. The participants will be admitted in the clinic on Day –1 and the study product will be administered on Day 1. The participants will remain in the clinic for approximately 8 hours for study-related procedures after study product administration and will be followed up for 24 weeks.

Safety laboratory samples will be collected throughout the study as per the SoA. The primary endpoint of ISR will be evaluated at specified time points up to Day 7; study participants will keep a diary of ISRs for 14 days after study product administration. Symptoms, maximum intensities, and durations will be reported through end of study to characterize presentation and resolution of local ISRs.

Safety review decisions and the status of the enrollment process will be shared with the Safety Review Team (SRT) in regular intervals and discussed during the monthly SRT meetings.

In Part 2, approximately 8 participants will receive a single 60 mg/kg IV dose of GSK3810109. A sentinel cohort of 2 participants will be used to mitigate the risk of unexpected AEs prior to dosing of the remaining 6 participants, who will be dosed in sequential cohorts of 2 participants each.

The sentinel cohort of these 2 participants will be admitted to the clinic on Day –1. The study product will be administered on Day 1 and participants will remain in the clinic and be monitored for 7 days after study product administration. The participants will be discharged from the clinic on Day 8 and will be followed up for 24 weeks.

Following Day 10 visit, core SRT will review the safety data (safety laboratory data, ECG, and AEs) from the sentinel cohort and may recommend continuation of the study where the next cohort of 2 participants will be dosed.

[figure not shown]

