### 1.1. Objectives, Estimands, and Endpoints

Objectives	Endpoints
Primary	

 
To evaluate the safety and tolerability of a single dose of GSK3810109 administered SC with rHuPH20 or IV in healthy adult participants
 
	
Part 1 (SC injection)
 
 
The number and percentages of participants who have AEs (Grade 2 or higher) and SAEs following GSK3810109 SC administration through Week 24
 
The number and percentages of participants who have ISRs within 7 days following GSK3810109 SC administration
 
The incidence of Grade 2 to 4 elevated ALT/AST following GSK3810109 SC administration
 
 
Part 2 (IV infusion)
 
 
The number and percentages of participants who have AEs and SAEs following GSK3810109 IV administration through Week 24
 
The incidence of Grade 2 to 4 elevated ALT/AST following GSK3810109 IV administration through Week 24
 

Secondary	

Objectives	Endpoints

 
• To evaluate the PK of a single dose of GSK3810109 administered SC with rHuPH20 or IV in healthy adult participants
 
	
 
• Assessment of PK parameters including AUC(0-inf), AUC(0-t), Cmax, Tmax, and t1/2 (if possible)
 

 
• To assess the severity and acceptance of pain and ISRs after SC administration of GSK3810109 with rHuPH20
 
	
 
• Dimension score “acceptance of ISRs” and individual item score assessing pain at Day 2 and Day 7 using the PIN Questionnaire
 

	
 
• Proportion of participants who are bothered or affected by the pain and local reactions as a result of the injection as measured by the PIN on Days 2 and 7
 

	
 
• Post-injection pain assessment using NRS at Days, 1, 2, and 7
 

	
 
• The incidence and duration of ISRs assessed overall and by grade including the duration at grade
 

 
• To assess the severity of pain after IV administration of GSK3810109
 
	
 
• Post-injection pain assessment using NRS at Days, 1, 2, and 7
 

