The number and percentage of participants who have ISRs within 7 days following study product administration will be provided for parts 1 and 2. Multiple symptoms of injection site reactions will be reported as separate AEs for each reported symptom. The number and percentage of participants who have ISRs will be summarized by preferred term and by the following classifications: 'Injection Site Abscess', 'Injection Site Anesthesia', 'Injection Site Bruising', 'Injection site cellulitis', 'Injection site discoloration', 'Injection site discomfort', 'Injection site erosion', 'Injection site erythema', 'Injection site hematoma', 'Injection site hemorrhage', 'Injection site itching', 'Injection site induration', 'Injection site nodule', 'Injection site pain', 'Injection site pressure', 'Injection site soreness', 'Injection site swelling', 'Injection site tenderness', 'Injection site warmth', and 'Other'. The incidence and duration of injection site reaction AEs overall and by grade, including the time at grade, will be summarized. All ISR AEs of a participant and the corresponding length of time of events will be considered for the summary table. If there are multiple events at each grade, the length of time would be equal to the average of all event times at a grade. Participants will be included in each grade level for which they had an event.

The ISR AEs will also be summarized by each preferred term for the following variables presenting the number and percentage of participants in each category: any grade and maximum grade (1, 2, 3, 4, and 5), maximum duration (1-7, 8-14, and >14 days), outcome, and number of

events (0, 1, 2, 3, 4, 5, 6-10, 11-15, 16-20, and >20 days). In addition, an event-level summary of injection/infusion site reaction AEs by preferred term will be created which includes the following information: any grade (1, 2, 3, 4, and 5), outcome, duration, and time to onset. Duration and time to onset will be analysed as continuous variables while number and percentage will be presented for the categories of other variables.

Injection Site Reactions (ISRs)

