

• ISRs will be presented by preferred term and according to the following classifications:

○ Injection site abscess

○ Injection site anesthesia

○ Injection site bruising

○ Injection site cellulitis

○ Injection site discoloration

○ Injection site discomfort

○ Injection site erosion

○ Injection site erythema

○ Injection site hematoma

○ Injection site hemorrhage

○ Injection site itching

○ Injection site induration

○ Injection site nodule

○ Injection site pain

○ Injection site pressure

○ Injection site soreness

○ Injection site swelling

○ Injection site tenderness

○ Injection site warmth

○ Other injection site reactions

• Time to onset (day) of ISRs relative to injection will also be presented, where the time to onset (day) will be calculated as follows: ISR Start Date – Date of Injection + 1

• For ISR duration by grade (where grade is as specified by investigators in the eCRF), the interval between a change in grade will be assigned to the previous grade, or the grade at the start of the interval

The number and percentage of participants with Grade 2 to 4 ALT or Grade 2 to 4 AST values will be provided by study part.

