Serum concentration-time data will be listed for each participant and summary statistics will be calculated (i.e. arithmetic mean, 95% CI, standard deviation, CV%, median, minimum and maximum) by study part and planned sampling time. Individual serum concentrations will be plotted by treatment and nominal time on both linear and semi-logarithmic scales. Mean and median serum concentrations will be plotted by treatment and nominal time on both linear and semi-logarithmic scales.

The PK analyses will be based on (1) the PK Concentration Analysis Set for assessment and characterization of PK concentrations and (2) the PK Parameter Analysis Set for assessment and characterization of PK parameters.

*Definition of Other Secondary Endpoints (Safety and Questionnaire Data):*

Acceptance of ISRs and Individual Item Score Assessing Pain (Part 1 only): Acceptance of ISRs is assessed by the responses to Questions 17 and 18 of the PIN questionnaire. Dimension score is computed as the average of responses to Questions 17 and 18. Response to question 3 will be used to assess pain.

Bothered or Affected by Pain/Local Reactions (Part 1 only): Assessed based on the responses to each item in the PIN questionnaire and domain scores. The number and proportion of participants in each response category will be evaluated and domain scores will be summarized.

Post-Injection Pain Assessment: NRS responses will be used to assess pain after injection. The number and percentage of participants in each response level will be assessed.

Incidence and Duration of ISRs (Part 1 only): Number and proportion of patients who had ISRs will be evaluated. Duration of ISRs will be computed as the time between start and end of an ISR, inclusive of both start and end dates (end date-start date+1).

Change from baseline in Clinical laboratory assessments, ECGs, and vital sign measurements: The change from baseline will be assessed for each clinical laboratory, ECG, and vital sign assessments.

*Other Secondary Endpoints Analyses:*

All analyses for secondary safety and questionnaire data endpoints will be performed using the Safety Analysis Set. Estimands are presented in [Section 1.1](#).

Questionnaire Assessments:

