#### Individual Item Scores

- Items are rated on a 5-point scale, ranging from 1 **CCI** to 5 **CCI**  

- Higher scores represent worse perception of injection.

Post-injection pain assessment scores based on a NRS from 0 to 10 (0: **CCI**, 10: **CCI**) will be summarized by the study day. NRS assessment scores will be reported by study part. The number and percentage of participants with each pain assessment score will be reported.

For part 1 only, number and percentage of participants reporting ISRs overall and by grade will be provided. The time to onset and duration of the ISRs will be summarized overall and by grade.

All data from PIN and NRS questionnaire assessments will be listed.

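### ISR time at grade is a within-participant mean event duration, so it falls when a shorter same-grade symptom is added and does not count the participant's days at that grade

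*SAP*

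**What the plan says.** **Endpoint.** For the subcutaneous part, SAP 1.1 names this secondary endpoint: "The incidence and duration of ISRs assessed overall and by grade including the duration at grade". Protocol 4.1 says that "durations will be reported through end of study to characterize presentation and resolution of local ISRs".

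**Unit of analysis.** SAP 4.2.2: "Multiple symptoms of injection site reactions will be reported as separate AEs for each reported symptom". SAP 4.3.1 defines duration per reaction: "Duration of ISRs will be computed as the time between start and end of an ISR", counted as end date minus start date plus one.

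**Combining events at a grade.** Where a participant has more than one event at a grade, SAP 4.2.2 says "the length of time would be equal to the average of all event times at a grade", and "Participants will be included in each grade level for which they had an event". The ISR box in the same section deals with grade changes: "the interval between a change in grade will be assigned to the previous grade, or the grade at the start of the interval".

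**Overall duration.** SAP 4.3.1, for Part 1: "The time to onset and duration of the ISRs will be summarized overall and by grade". The averaging rule is written for time at a grade. No sentence says how one participant's several events combine in the overall row.

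**Other ISR duration outputs.** SAP 4.2.2 also plans, for each preferred term, the participant's maximum duration in three bands (1-7, 8-14 and over 14 days), and an event-level summary with duration as a continuous variable. All adverse events are listed.

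**The concern.** One injection can produce several concurrent events, such as redness, pain and itching. A reader of a row labelled time at grade will probably take it as how long participants had a reaction of that grade. The planned statistic answers a different question, namely how long a typical event lasted within a participant. The two can move in opposite directions: a participant with more symptoms can show a shorter time at grade.

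This bears on a named secondary endpoint in a part with about 8 participants, where one person can shift a group mean noticeably. Long reactions are plausible. Protocol 2.2.1 describes an erythema in the first-in-human study that took 30 days to resolve, and Protocol 2.3.1.1 says that some ISRs lasted up to 6 weeks.

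**Working it through.** The documents give no figure to reproduce, so the check applies the SAP's own rules to example patterns. The 30-day length matches the erythema in Protocol 2.2.1. All other durations and all grade intervals are assumptions.

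**Step 1. Direction of the gap.** For the events at one grade: mean event time ≤ longest event ≤ distinct calendar days covered. The mean therefore never exceeds the days at that grade. Equality needs all events to be equally long and the longest to cover every day, that is, one event or identical days.

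**Step 2. Same grade, same start.**

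| Events (days) | Planned value | Distinct days |
|---|---|---|
| 30 | 30 | 30 |
| 30, 2 | (30+2)/2 = 16 | 30 |
| 30, 2, 1 | (30+2+1)/3 = 11 | 30 |

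**Step 3. Overlap.** Take two 5-day events at one grade, the second starting k days after the first. The planned value is always 5. Distinct days are 5+k for k = 0 to 5, and 10 from then on.

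**Step 4. A fading reaction.** Suppose a 30-day erythema is Grade 3 on days 1-7, Grade 2 on days 8-14 and Grade 1 on days 15-30, with Grade 1 pain on days 1-2 and Grade 1 pruritus on day 1.

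- Grade 1, planned value: (16+2+1)/3 = 6.3 days.
- Grade 1, distinct days: 16+2 = 18.
- Grades 2 and 3: 7 days each on both measures.
- Any ISR: 30 distinct days. The plain mean of the three events is (30+2+1)/3 = 11.
- The difference at Grade 1 is 18 - 6.33 = 11.67 days. If 2, 4 or 8 participants are in the Grade 1 row, the choice of measure for this one participant moves the row mean by 11.67/2 = 5.8, 11.67/4 = 2.9 or 11.67/8 = 1.5 days.

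**Step 5. Repeat spells.** One ISR is Grade 1 for 2 days, then Grade 2, then Grade 1 for 8 days. If the spells are added, time at Grade 1 is 10 days. If each spell counts as an event time, it is (2+8)/2 = 5. The SAP permits either reading.

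**Step 6. Could several symptoms occur together?** Protocol 2.2.1 reports, after SC dosing in 12 participants, pain/tenderness in 9, swelling in 4, redness in 6 and pruritus in 3, which is 22 symptom reports. If m participants had two or more of these four symptoms, then 22 ≤ 4m + (12 - m), so m ≥ 10/3. At least 4 of 12 had several. At that rate, the chance of at least one such participant among 8 is 1 - (2/3)^8 = 96%. This shows how often the rule could apply. The documents do not say how many of these symptoms shared a grade.

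**The case against.** The strongest defence is that the plan does what it says. SAP 4.3.1 defines duration per reaction, and no passage defines duration at grade as days with any reaction. A within-participant average of event durations is a valid summary under that definition. The Protocol 4.1 sentence also covers symptoms and maximum intensities, and SAP 4.2.2 delivers these by preferred term. A count of days pooled across symptoms would be an added variable. All of this stands, which is why the average should be kept. What does not stand is the label: a row called time at grade will be read as days.

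A reader might go further, and the documents do not support these stronger readings:

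- *Days at grade are never reported.* With a single event and a single spell at a grade, the planned value is exactly the days at that grade.
- *Long reactions are hidden.* A 30-day erythema falls in the over-14-day band of the maximum-duration table whatever else is added, and it appears in the event-level summary and the listing. These outputs do not supply the count, however. The maximum is banded, per symptom and limited to the longest event, the event-level summary has no participant dimension, and a listing is not a summary.
- *The severe grades are distorted.* In the first-in-human study (Protocol 2.2.1) pain and pruritus were mild only, swelling was at most moderate, and only redness was severe. On that pattern, averaging across symptoms touches Grades 1 and 2, not Grade 3.
- *The number-of-events bands, which carry the unit days, are a day count.* The variable is named as a count of events, so the unit looks like a slip.
- *Partial end dates bias durations.* SAP 6.2.5 already bars imputed dates from duration, and no defect is shown.

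The Step 4 contrast also depends on the comparator. Counting each day only at its worst grade gives 16 Grade 1 days instead of 18. The gap to 6.3 remains. The silence on overall duration and on repeat spells is a gap in wording. The output specification, to which the SAP leaves display details, might address it but is not available here.

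**Conclusion.** The point holds as a cheap improvement to a descriptive secondary endpoint. Under SAP 4.2.2, time at grade is a mean event duration. It can understate the participant's days at a grade but cannot overstate them, and no other planned summary gives those days when there are several events. In the examples the planned value is 11 or 16 against 30 days, and 6.3 against 18. These sizes rest on assumed durations and on symptoms sharing a grade, so they show what can happen and do not predict it. The primary 7-day ISR incidence does not use duration and is unaffected. No hypothesis is tested.

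**What to change.** In SAP 4.2.2:

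1. Keep the pre-specified average and label it mean event duration.
2. Add, for each participant, the number of distinct calendar days with any ISR, and with at least one ISR at each grade.
3. Note that one day can count at more than one grade when symptoms differ, so the grade rows need not sum to the any-ISR row.
4. State in one sentence how several events of a participant are combined for overall duration.
5. State in one sentence whether repeat spells of one event at the same grade enter the mean separately or added together.

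The cost is SAP wording, one extra derivation and one extra table row per grade plus one for any ISR, all from dates and grades already collected. The downside is two duration measures side by side, with grade rows that can add to more than the any-ISR days. In Step 4 they give 7+7+18 = 32 against 30, because days 1-2 count at both Grade 1 and Grade 3.

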### **4.3. Secondary Endpoint(s) Analyses**

#### **4.3.1. Supportive secondary endpoint(s)**

##### **Definition of Secondary PK Endpoints:**

The following serum PK parameters of GSK3810109 will be determined as data permit:

AUC(0-inf): Area under the serum concentration-time curve from time zero (pre-dose) extrapolated to infinite time; to be calculated using the linear trapezoidal rule for each incremental trapezoid and the log trapezoidal rule for each decremental trapezoid.

AUC(0-t): Area under the serum concentration-time curve from time zero (pre-dose) to the time of the last quantifiable concentration; to be calculated using the linear trapezoidal rule for each incremental trapezoid and the log trapezoidal rule for each decremental trapezoid.

Cmax: Maximum observed serum concentration determined directly from the concentration-time data.

Tmax: Time to reach maximum observed serum concentration

t1/2: Apparent terminal phase half-life (if possible)

Additional PK parameters may be calculated as data permit:

CL/F: Apparent total body clearance following extravascular administration

CL: Total body clearance following intravenous administration

Vz/F: Apparent volume of distribution following extravascular administration

Vss: Volume of distribution at steady state calculated for intravenous administration

*PK Analyses:*

Pharmacokinetic parameters will be calculated by standard non-compartmental analysis according to GSK guideline VQD-GUI-000722 (6.0): Non-Compartmental Analysis of Pharmacokinetic Data and using the currently supported version of Phoenix WinNonlin (8.0 or higher) or using the currently supported version of SAS (9.4 or higher). All calculations of non-compartmental parameters will be based on actual sampling times.

Summary statistics (arithmetic mean, geometric mean, median, 95% CI [arithmetic and geometric], standard deviation [arithmetic and on ln-scale], minimum, maximum, and geometric between-participant CV (%CVb) for serum PK parameters will be summarized.

Serum concentration-time data will be listed for each participant and summary statistics will be calculated (i.e. arithmetic mean, 95% CI, standard deviation, CV%, median, minimum and maximum) by study part and planned sampling time. Individual serum concentrations will be plotted by treatment and nominal time on both linear and semi-logarithmic scales. Mean and median serum concentrations will be plotted by treatment and nominal time on both linear and semi-logarithmic scales.

The PK analyses will be based on (1) the PK Concentration Analysis Set for assessment and characterization of PK concentrations and (2) the PK Parameter Analysis Set for assessment and characterization of PK parameters.

*Definition of Other Secondary Endpoints (Safety and Questionnaire Data):*

Acceptance of ISRs and Individual Item Score Assessing Pain (Part 1 only): Acceptance of ISRs is assessed by the responses to Questions 17 and 18 of the PIN questionnaire. Dimension score is computed as the average of responses to Questions 17 and 18. Response to question 3 will be used to assess pain.

Bothered or Affected by Pain/Local Reactions (Part 1 only): Assessed based on the responses to each item in the PIN questionnaire and domain scores. The number and proportion of participants in each response category will be evaluated and domain scores will be summarized.

Post-Injection Pain Assessment: NRS responses will be used to assess pain after injection. The number and percentage of participants in each response level will be assessed.

Incidence and Duration of ISRs (Part 1 only): Number and proportion of patients who had ISRs will be evaluated. Duration of ISRs will be computed as the time between start and end of an ISR, inclusive of both start and end dates (end date-start date+1).

Change from baseline in Clinical laboratory assessments, ECGs, and vital sign measurements: The change from baseline will be assessed for each clinical laboratory, ECG, and vital sign assessments.

*Other Secondary Endpoints Analyses:*

All analyses for secondary safety and questionnaire data endpoints will be performed using the Safety Analysis Set. Estimands are presented in [Section 1.1](#).

Questionnaire Assessments:

PIN questionnaire is only applicable for part 1 and is included in [Section 6.1.5](#). Responses to the PIN questionnaire items at Day 2 and Day 7 will be summarized separately using descriptive statistics. Acceptance of ISRs dimension score is computed as the average of scores for questions 17 and 18 of the PIN questionnaire. Number and percentage of participants reporting they were bothered or affected by the pain and local reactions based on the responses to the items in the PIN Questionnaire will be provided for Day 2 and Day 7. Responses to each item in the PIN questionnaire will be summarized presenting the number and proportion of participants in each response category. Additionally, domain scores will be calculated using the information below:

Dimension Score ( Chevat, 2008 )

 
• Domains and Clusters 
 
○ Bother from injection site reactions: items 3, 4, 5, 6, 7, and 8
 
○ Leg movement: items 11, 12, 15, and 16
 
○ Sleep: items 9, 10, 13, and 14
 
○ Acceptability: items 17 and 18
 
 
 
• 5 items not included in any of these domains and maintained as individual items (items 1, 2, 19, 20, and 21) (anxiety before, pain, satisfaction, anxiety after, and willingness)
 

- No overall score is calculated per the guidance in the Chevot, 2008 reference.
- The score of a domain is calculated as the mean of all non-missing items with the domain. Higher scores represent worse perception of injection
- A maximum of <50% items can be missing within a domain. Thus, if the number of missing items is  $\geq 3$  (Bother from injection site reactions),  $\geq 2$  (Leg movement/Sleep),  $\geq 1$  (Acceptability), then the total score for the domain should not be computed.

